6.2 Glucose-Lowering Medications

Diabetes review and medication management will be conducted by the treating physician starting from screening visits and throughout the study. The treating physician is a member of the site study team who has been expertise in managing patients with type 2 diabetes.

6.2.1 Background Glucose-Lowering Medications

Eligible participants must be on two to three non-insulin glucose-lowering medication(s), one at maximum tolerated dose and another at half-maximum dose at least, without a severe hypoglycemic event within the past six months of the screening visit.

Participant's background medication will be kept stable (no change in medication or dose) for at least 12 weeks prior to the Baseline Visit.

Peri-procedurally, the dose of medications with hypoglycemic risks will be adjusted per guidelines provided in **Section 6.2.2**.

Following the transitional diet period, participant's medication will be titrated to the background level and maintained stable until the Week 24 Visit has been completed. Medication and/or dose change necessary for managing hypoglycemia, hyperglycemia, or other safety concerns is permitted. Reason for the medication change must be documented on eCRF.

Following the Week 24 Visit, participants will be managed according to the current (2021) guidelines of the American Diabetes Association² and their glucose-lowering medications will be optimized as necessary to reach an HbA1c target of 7%.

Background medications are non-investigational products. They should be used in accordance with standard of care and their approved labeling. They will not be provided by the sponsor.

6.2.2 Guideline for Managing Hypoglycemic Risks

The following guideline is provided for minimizing hypoglycemic risks during the study. The treating physicians should exercise their clinical judgment for the treatment of individual patients.

6.2.2.1 Peri-procedure

The dose of sulfonylureas or meglitinides will be reduced by 50% (or discontinued if on the lowest recommended dose) one day before the index procedure to avoid potential hypoglycemic risks. If an episode of documented or symptomatic hypoglycemia is experienced during the peri-procedure or transitional diet period, further reduction of sulfonylurea or meglitinide dose by 50% or discontinuation if on the lowest dose should occur.

Metformin should be held the day prior to endoscopy and resumed post procedure when the patient tolerates oral intake.

SGLT2i should be held three (3) days prior to the index procedure and resumed when the patient transitions to normal diet (after the 2-week transitional diet period).

GLP-1 Receptor agonists and DDP-4 inhibitors should be held in the peri-procedure period if the subject experiences significant nausea and/or vomiting and can be resumed once symptoms resolve at the discretion of the principal investigator.

6.2.2.2 During Diet Transition Period

During the diet transition period, CGM data will be reviewed by the treating physician and used to guide medication titration.

If the risk of hypoglycemia has not been adequately reduced, doses of sulfonylureas, meglitinides, or possibly other glucose-lowering medication(s) should be further reduced or discontinued if appropriate and in the clinical judgment of the participant's treating physician.

In the event of severe hypoglycemia, study staff will document these episodes on the Adverse Event form.

6.2.3 Guidelines for Managing Hyperglycemia

After the background medications have been titrated back to baseline level following the transitional diet period, participants with severe, persistent hyperglycemia should be offered treatment intensification.

In the event of suspected persistent hyperglycemia in a subject based on either symptoms of hyperglycemia (eg, thirst, polyuria, blurred vision), CGM readings of >250 mg/dL for > 30% of the time, or repeated fasting CGM readings above 270 mg/dL (e.g. occurring 3 days in a week), the investigator should perform additional laboratory tests to assess whether rescue therapy is warranted.

Participants meeting the following criteria should be offered rescue medication (i.e. intensification of glucose-lowering background medication and/or initiation of basal insulin).

- FPG > 270 mg/dL, confirmed by repeated measures more than 3 days apart, and no intercurrent cause can be identified, or
- HbA1c is >8.0% AND the interval improvement is <0.5% from baseline, by Week 12

After Week 24, participants should be offered treatment intensification if they do not reach their HbA1c target, which for most individuals is 7.0%.

The above criteria and medications are provided as a guideline. Investigators should always exercise his/her clinical judgement based on individual conditions to protect participant's safety and wellbeing.

Participants who meet rescue criteria before Week 24 should first complete the Week 24 visit activities within 5 days before initiation of the rescue medication to ensure that important trial endpoint measurements are collected and be provided the rescue therapy.

Medication changes and reasons for the changes will be documented on the eCRFs. Medications used to manage hyperglycemia are non-investigational and will not be provided by the sponsor.

6.3 Proton Pump Inhibitor

Participants will be placed on PPI (Omeprazole 40 mg daily or equivalent) at least one week prior to the index procedure.

6.4 NSAIDs (Non-Steroidal Anti-inflammatory Drugs)

Participants must be off NSAIDs for four weeks after the index procedure. Low dose aspirin (81 mg/day) may be used if needed in combination with prophylactic PPI. If unable to discontinue NSAID for four weeks, the participant should be excluded from the study.

6.5 Anticoagulant and Antiplatelet Medications

If a participant is taking anticoagulant or antiplatelet medications, the anticoagulant must be stopped until the International normalized ratio (INR) returns to normal or bridged with low molecular weight heparin (LMWH) prior to the index procedure. The antiplatelet medications must be stopped for 7 days prior to the index procedure. Post procedure, the anticoagulant or antiplatelet medications may be resumed after 48 hours if there is no evidence of bleeding.

The investigator must evaluate the risks of discontinuing these medications based on the overall clinical judgement. If these medications can't be discontinued safely, the participant should be excluded from the study.

6.6 Prohibited Concomitant Medications

6.6.1 Weight-Loss Medications

Study participants will not be allowed to take any weight-loss products during the course of the study, including prescription or over-the-counter (OTC) weight loss medications and herbal products.

6.7 Other Concomitant Medications

For participants on oral thyroid replacement therapy, TSH should be tested at month 3, 6, 9, and 12, and medication adjusted as necessary per clinical guidelines.

Concomitant medications deemed medically necessary for the participant will be allowed during the course of the study; however, any changes in medications will be documented on the Concomitant Medication Log. Medications used during the DMR procedure, such as anesthesia, will not be tracked via the Concomitant Medication Log.

6.8 Participant Education and Lifestyle Counseling

6.8.1 Hypoglycemia

At the onset of the study, participants will be provided a Freestyle Libre 2 CGM device and an instruction (**Appendix** 4) on how to monitor glucose levels during the study. Participants should be educated on the potential for development of hypoglycemia, the symptoms and signs of hypoglycemia, the use of CGM and how to detect hypoglycemia, and instruction on treating hypoglycemia. Participants (especially those receiving a sulfonylurea) should be instructed to monitor for hypoglycemia.

Symptoms suggestive of hypoglycemia include lightheadedness, tremor, shaking, sweating, tingling, blurred vision, difficulty concentrating, and confusion. With marked hypoglycemia, patients may develop altered consciousness, coma, or seizures.

Participants will use CGM for at least 5 days at baseline and for 48 weeks after the procedure.

Participants should also be instructed to confirm blood glucose level with a finger stick if they receive CGM alerts indicating hypoglycemia and contact his/her treating physician to discuss whether the dosage of glucose-lowering medication(s) should be adjusted to prevent hypoglycemic events.

Participants should also be instructed to promptly contact site staff if they experience symptoms of hypoglycemia, CGM readings of <70mg/dL for >4% of time¹¹, or CGM readings of <54 mg/dL for >1% of time¹¹.

6.8.2 Hyperglycemia

Participant should be instructed to contact site staff in the event of suspected persistent hyperglycemia based on symptoms of hyperglycemia (e.g, thirst, polyuria, blurred vision), CGM readings above 250 mg/dL for >30% of time, or repeated fasting CGM readings >270 mg/dL (e.g. occurring 3 days in a week).

The investigator will perform additional laboratory tests as necessary to further investigate and may decide to offer rescue medications as necessary per Section 6.2.3.

6.8.3 Transitional Diet

Participants will be educated on the post-procedure transitional diet comprised of 24 hours of clear liquids (water, clear broth, sugar-free popsicles, tea) followed by a full liquid diet (dairy-free milk, protein shakes, strained soups) for 3 days, pureed food diet (pureed soup, sugar-free pudding, fat-free yogurt) for 3 days, and soft food diet (such as stew, fish, soft lean meat) for one week, and then transition to a normal diet as tolerated. Participants should be educated on the importance of hydration, especially during the transitional diet period to prevent hypovolemia. Participants should be instructed to contact the study team if s/he is unable to take food and unable to take at least 2 liters of water per day. Participants should also be instructed to avoid dairy products if experiencing any diarrhea during the transitional diet period.

6.8.4 Lifestyle Modification Counseling

The lifestyle modification counseling will follow standard of care as outlined in the Standard of Medical Care in Diabetes 2021². The goal is to promote use and adherence to healthy eating patterns, increase physical activity (primarily through daily walking), and to recommend behavioral modification strategies.

6.8.4.1 Nutritional Recommendations

Participants will be educated on healthful eating patterns to improve overall health, emphasizing a variety of nutrient-dense foods in appropriate portion sizes. The nutritional recommendations will be individualized to achieve and maintain healthy body weight goals; to attain individualized glycemic control, and blood pressure, and lipid goals; and to delay or prevent the complications of diabetes. Participants will be educated on controlling portion sizes and intake of carbohydrates/starchy foods; increasing intake of low glycemic index and high-protein foods, as well as vegetables; and reducing intake of foods high in fat and sugar, and alcohol. The calorie recommendation will follow the recommendations of the Diabetes Prevention Program¹². Participants who weigh \leq 114 kg (\leq 250 lb) will be prescribed 1200-1500 kcal/d and those > 114 kg (> 250 lb) 1500-1800 kcal/d.

6.8.4.2 Physical Activity Recommendations

Participants will be encouraged to include more physical activity in their daily routine for example: walk more every day, climb the stairs instead of taking the lift or escalators, walk to the next bus stop, walk to shops, ride an exercise bike while watching TV. They will also be encouraged to do more activity in their leisure time such as: going for a walk, bicycling or swimming. They will be asked to start with short periods

of low-intensity exercise and increase the intensity and duration slowly. Their goal will be to include 150 minutes a week of moderate intensity and 75 minutes a week of vigorous intensity aerobic activity and muscle strengthening activities more than 2 days a week. Tools such as pedometers or mobile apps maybe recommended (but are not provided) to help individuals increasing their exercise. Any exercise will be adjusted to individual needs and activity levels.

Because of the variation in glycemic response to exercise bouts, participants who are on medications with hypoglycemic risks should be educated to check glucose levels before and after periods of exercise and about the potential prolonged effects (depending on intensity and duration).

6.8.4.3 Behavior Modification

At the same time as the nutritional recommendations and activity advice, participants will be instructed in behavioral modification strategies to promote adherence. Examples of these strategies include estimating portion size by using diabetes plates, reducing consumption of high sugar, high calorie beverages, putting the fork down between bites, etc.

CGM data will be reviewed with the participant to educate the participant as to what food choices minimize postprandial plasma glucose (PPG) and what physical activity choices directly lower PPG; troubleshoot for those with glucose out of their desired range; and reinforce choices that resulted in desirable glucose consequences.

7 STUDY EVALUATION AND STUDY VISITS

This protocol is developed at the time of the COVID-19 pandemic. To mitigate the risks of potential patient exposure, study assessments and visits may be performed remotely if necessary using the site's telehealth platform, and onsite visits can be limited to the ones necessary for study intervention and the integrity of the study. Participants will be provided with a scale to enable remote weight data collection. If necessary, nurse in-home visits may be used for in-home blood sample collections and vital signs data collection.

7.1 Demographics

Baseline demographic data will be collected to assess participant characteristics that include age, gender, race and ethnicity.

7.2 Medical History and Concomitant Medication

Participants' medical history and baseline medications will be reviewed and documented at screening visit. Changes in medical condition and medication usage will be reviewed, assessed, and documented at each study visit.

7.3 Anthropometric measurements

For onsite visits:

Height is measured without shoes in centimeter or inch and recorded in the eCRF to the nearest ½ cm or ¼ inch.

Body weight should be measured in kilograms (kg) or pound (Ib), to one decimal, without shoes and only wearing undergarments and an exam gown.

The BMI is calculated in the eCRF using the following

BMI = body weight (kg)/(height (m) x height (m)) $[kg/m^2 = lb/in^2 x 703]$.

Waist circumference is measured with the participant in a standing position with arms down their side and feet together. The measurement is taken at the midway between the lower rib margin and the iliac crest using a non-stretchable measuring tape. The tape should touch the skin but not compress soft tissue. The participant should be asked to breathe normally and the measurement should be taken when the participant is breathing out gently.

The measurement will be recorded to the nearest ½ cm or ¼ inch using the same measuring tape throughout the trial.

For remote visits:

Participants will be provided with a scale to enable weight assessment at home. Participants will be instructed to wear only undergarments and no shoes when measuring weight.

Waist circumference will be measured by the nurse who also performs in-home blood sample collection.

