7.4 Vital Signs

Systolic and diastolic blood pressure, pulse rate and respiratory rate should be measured in a sitting position after the participant has been resting for at least 5 minutes and by using standard clinical practice at the trial site. For remote visits, the measurements will be performed by a nurse who also performs in-home blood sample collection.

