This visit will be performed onsite. The following evaluations/procedures are to be performed. Participant's study eligibility will be reconfirmed at this visit.

- Physical examination
- Anthropometric measurements including height, weight and waist circumference
- Vital signs
- Adverse event (changes in medical history)
- Concomitant medications
- 12-lead EKG
- Laboratory tests:
 - o Hematology (CBC with differentials)
 - Metabolic panel
 - o Glycemic parameters (HbA1C, MMTT, HOMA-IR)
 - Fasting lipid panel
 - o Lipase, Amylase
 - o Serum iron, ferritin, transferrin, saturation, serum folate, Vitamin D, Vitamin B12
 - o International normalized ratio (INR) for participants on Warfarin (may be performed on Day 0)
- H. Pylori breath or stool test
- Pregnancy test for females capable of becoming pregnant
- Assessment for eligibility
- Preparation with gastroenterologist for procedure, medication management per Section 6.
- Diabetes education, including instruction on CGM use
- Treating physician review of diabetes history and titration of glucose-lowing medications per Section 6.2
- Review CGM data
- Lifestyle counselling

If the participant is no longer eligible for the study due to a change in the participant's condition, such as pregnancy, abnormal blood test values, HbA1C outside of the protocol range, or weight change resulting in a BMI outside of the protocol range, the participant will be excluded from the study and documented as a screen failure.

The screening and baseline visit may be combined if the screening visit falls within the baseline visit window. In this case, data collected during the combined visit will serve as both screen and baseline data.

It is recognized that new COVID-19 restrictions may cause delays in scheduling the index procedure, resulting in the baseline visit out of window. In case the baseline visit is out of visit window, investigator will reassess participant's eligibility by evaluating any changes in participant's medical history and medications, Investigator's assessment will be documented on eCRF. The following tests will be repeated for safety considerations or to serve as baseline data:

- Laboratory tests:
 - Hematology (CBC with differentials)
 - o Glycemic parameters (FPG, HbA1C, insulin, HOMA-IR)
- Pregnancy test for females capable of becoming pregnant (may be performed on Day 0)
- Anthropometric measurements including weight and waist circumference (may be collected on Day
 0)

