7.13.4 Follow-up Visits

Study follow up visits will be performed at Week 1, 2, 4, and every 4 weeks thereafter. The last study visit is Week 48. The visit windows and assessments/procedures to be performed at each visit are shown in SoA (**Appendix 2**).

To minimize COVID-19 risks, follow up visits may be performed remotely if necessary as below (note: "at home" denotes to participant's home or location of choice). Onsite visit is preferred and will not be considered as a protocol deviation.

- Body weight may be measured at home using the scale provided to participants
- Vital signs and waist circumference may be measured by a visiting nurse at home
- Testing samples (blood, stool, urine) may be collected by a visiting nurse at home
- Assessment of AEs, medication changes, CGM and diabetes review may be performed remotely using site's virtual visit platform
- Lifestyle modification counseling may be performed remotely at each visit.

If situation permits, visits at Week 24 and 48 should be performed onsite. However remote visits at these timepoints will not be considered as protocol deviation.

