### **Ninth Secondary Endpoint**

The distribution of this endpoint is binary. Proportion of treated patients who achieve a HbA1c improvement of  $\geq 0.5\%$  or more at 24 weeks from baseline and maintained at 48 weeks. Patients who fail to maintain HbA1c improvement  $\geq 0.3\%$  at 48 weeks, for any reason, will be counted as not having achieved this endpoint. Patients who fail to achieve a HbA1c  $\geq 0.5\%$  at 24 weeks will be excluded from the tabulation. The primary population for analysis of this endpoint will be the FAS population.

Proportion of treated patients with an HbA1c improvement  $\geq 0.5\%$  from baseline at 24 weeks maintained at 48 weeks.

**Tenth Secondary Endpoint:** The distribution of this endpoint is continuous. The primary population for analysis of this endpoint will be the FAS population. Change in weight from baseline (post-baseline minus baseline) by visit. Weight change will be reported in both kilograms and %TBWL.

**Eleventh Secondary Endpoint:** Change in glucose-lowering medication usage.

**Twelfth Secondary Endpoint:** The distribution of this endpoint is continuous. The primary population for analysis of this endpoint will be the FAS population. Change in liver enzyme from baseline at 24 weeks (post-baseline minus baseline) for Alanine Aminotransferase (ALT).

**Thirteenth Secondary Endpoint:** The distribution of this endpoint is continuous. The primary population for analysis of this endpoint will be the FAS population. Change in liver enzyme from baseline at 24 weeks (post-baseline minus baseline) for Aspartate Aminotransferase (AST).

Version 1.0 Confidential Page 31 of 42

**Fourteenth Secondary Endpoint:** The distribution of this endpoint is continuous. The primary population for analysis of this endpoint will be the FAS population. Change from baseline in blood pressure by visit (systolic and diastolic run separately).

**Fifteenth Secondary Endpoint:** The distribution of this endpoint is continuous. The primary population for analysis of this endpoint will be the FAS population. Change in lipid profile from baseline by visit: total cholesterol

**Sixteenth Secondary Endpoint:** The distribution of this endpoint is continuous. The primary population for analysis of this endpoint will be the FAS population. Change in lipid profile from baseline by visit: triglycerides

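### Clinic and home weights follow different dress rules and use different scales, yet the SAP subtracts the clinic baseline from both without regard to setting

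*Protocol*

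**What the plan says.** Protocol 7.3 gives two procedures for body weight. Onsite, it is measured "without shoes and only wearing undergarments and an exam gown". For remote visits, "Participants will be provided with a scale to enable weight assessment at home", and "Participants will be instructed to wear only undergarments and no shoes when measuring weight". Neither document describes a calibration of the home scale, a comparison with the site scale, or a baseline reading on the home scale.

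On the baseline visit, Protocol 7.13.2 states: "This visit will be performed onsite". If that visit falls out of window, the repeat weight may be taken on Day 0, the procedure visit. For follow-up, Protocol 7.13.4 states: "Body weight may be measured at home using the scale provided to participants". The same section prefers onsite visits, asks for Weeks 24 and 48 onsite where possible, and says a remote visit at those weeks is not a deviation.

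Appendix 2 collects weight at Weeks 1, 4, 12, 24, 36 and 48. It codes Weeks 1, 4, 12 and 36 as clinic or remote, and Weeks 24 and 48 as clinic. SAP 8.6 codes Weeks 1 and 12 as remote, and Weeks 4, 24, 36 and 48 as clinic.

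For the tenth secondary endpoint, SAP section 9 specifies: "Change in weight from baseline (post-baseline minus baseline) by visit. Weight change will be reported in both kilograms and %TBWL". Neither that entry nor SAP 9.2 distinguishes clinic from home weights. The repeated-measures model in Protocol 12.4.4 names time and treatment arm only, and SAP 7.2 plans no stratification factors.

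**The concern.** A change score is free of measurement artefact only if both readings are taken the same way. Here the first reading includes a gown and comes from the site scale. A later home reading has no gown and comes from another scale. The gown part always points toward loss, which is the favourable direction.

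The study has no control arm, so a difference between settings cannot cancel out of the overall estimate. It could cancel between device groups only if each group had the same share of home weights at each visit. The plan does not arrange for that, and the groups were treated in sequence. SAP section 3 gives their sizes as 3, 7 and 10, so a few readings can move a group mean. If visits follow the coding in SAP 8.6, the by-visit series also alternates between settings, and part of any apparent time trend would be an artefact.

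**Working it through.** The plan states no target, standard deviation or power for weight, so there is no figure of its own to reproduce. The error is worked out directly.

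**Inputs from the documents**
- Dress: undergarments plus gown onsite, undergarments only at home (Protocol 7.3). The difference is the gown alone.
- Baseline: onsite (Protocol 7.13.2).
- Benchmark: a mean loss of 2.5 kg at 24 weeks in the second hydrothermal resurfacing study cited in Protocol 1.2.
- Group sizes: 3, 7 and 10 (SAP section 3).

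**Assumptions, not in the documents**
- Gown weight g: 0.1 to 0.5 kg.
- Home scale minus site scale, s: −1.0 to +1.0 kg, sign unknown.
- Share weighed at home at a visit, f: 25%, 50% or 100%.

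**Formulas**
- Spurious change for one home weight: −g + s.
- Mean gown bias at a visit: −g × f.

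**Gown term against the benchmark.** 0.1/2.5 = 4% and 0.5/2.5 = 20%.

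**Gown term by share weighed at home**

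| Share f | g = 0.1 kg | g = 0.5 kg | Share of 2.5 kg |
|---|---|---|---|
| 25% | −0.025 kg | −0.125 kg | 1% to 5% |
| 50% | −0.05 kg | −0.25 kg | 2% to 10% |
| 100% | −0.1 kg | −0.5 kg | 4% to 20% |

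**As a percentage of body weight.** BMI 32 is the midpoint of the eligible range of 24 to 40. With an assumed height of 1.70 m, weight is 32 × 1.70² = 92.5 kg. Then 0.1/92.5 = 0.11% and 0.5/92.5 = 0.54%.

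**Adding the scale term**
- Most negative: −0.5 − 1.0 = −1.5 kg.
- Most positive: −0.1 + 1.0 = +0.9 kg.
- The error is zero when the home scale reads high by exactly the gown weight (s = g).

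**Scale term at group level.** Assume independent home scales, an offset standard deviation of 0.5 to 1.0 kg and every member weighed at home. The mean offset then has standard deviation SD/√n:
- n = 3: 0.29 to 0.58 kg
- n = 7: 0.19 to 0.38 kg
- n = 10: 0.16 to 0.32 kg
- n = 20: 0.11 to 0.22 kg

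These are worst cases, because they take f = 100%.

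**Which visits are exposed.** Weeks 1 and 12 are coded remote in SAP 8.6. Weeks 4 and 36 are exposed only where the remote option in Appendix 2 is used. Weeks 24 and 48 are planned onsite, so they are exposed only by exception.

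**The case against.** The strongest reply is that exposure is limited. Protocol 7.13.4 allows remote follow-up only where necessary. The Week 4 endoscopy (Protocol 7.12) and the Week 12 and 48 meal tests (Protocol 7.9 and Appendix 2) normally bring the participant in, although both may be omitted because of COVID-19. Weeks 24 and 48 are planned onsite. Weight is one of 18 secondary endpoints in an unpowered feasibility study, SAP 7.1 treats testing as informative only, and the primary safety endpoint is untouched. All of this stands. It reduces the size of the problem, but it does not remove the mismatch where home weights are used.

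A reader might infer more than the documents support, in four ways.

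- **That remote visits will show weight loss that did not occur.** Only the gown term has a known sign. The scale offset may be larger and may go either way, so the net error could be loss, nothing or gain.
- **That the setting goes unrecorded.** The case report forms are not available here, and both schedules code visits by type. What can be said is that the SAP does not use setting in the weight analysis.
- **That the device groups will differ falsely.** This needs the share of home weights to differ between groups, and neither document gives that share.
- **That blood pressure has the same flaw.** Protocol 7.4 sets one seated, rested procedure, and "For remote visits, the measurements will be performed by a nurse who also performs in-home blood sample collection". No measurement rule differs, so the parallel does not hold.

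**Conclusion.** The point holds as a modest, avoidable measurement problem in one secondary endpoint. Followed as written, the plan builds the gown into every weight change that uses a home reading. With a gown of 0.1 to 0.5 kg, that is 0.1 to 0.5 kg toward loss at a visit where everyone is weighed at home, and half that at a visit where half are. An unchecked scale difference adds error of unknown direction. With offsets of up to 1.0 kg either way, the net error for a single home weight runs from −1.5 to +0.9 kg.

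The two dress rules, the two scales, the onsite baseline and the subtraction without regard to setting are all in the text. The gown weight, the scale offset and the share of home weights are assumptions. Weeks 24 and 48 should be largely unaffected if they are held onsite as planned.

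**What to change.** 1. In Protocol 7.3, use one dress rule for both settings. This sets the gown term to zero for weights taken under it.
2. Identify clinic or home for each weight in the analysis data.
3. For any participant not yet treated, take one paired reading on the supplied scale at the baseline visit and compute remote change from it. With the same dress rule, a constant scale offset then cancels. SAP section 3 reports enrolment in the past tense with all 20 participants counted, so this step may come too late.
4. In SAP endpoint 10, add an onsite-only (clinic-to-clinic) summary of weight change, with Weeks 24 and 48 as the principal timepoints. Show it alongside the by-visit table of all weights, with home values flagged.

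The onsite-only summary should be a sensitivity analysis and should not replace the full table. Dropping home weights altogether would cost too much information in groups of 3, 7 and 10.

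The cost is a sentence in the protocol, one variable, one extra reading where still possible, and one extra table, with fewer values in some of its by-visit rows.
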